9.2. Sample Size and Randomization

Sample size estimates are based on the primary trial outcome: # hospital transfers/person-days alive based on Medicare claims data), which include admissions, emergency department visits, and observation stays over a 12-month follow-up period among Medicare fee-for-service long-stay residents with advanced dementia or advanced COPD/CHF. Based on data from our partners' NHs in 2012 and 2013, we estimate that hospital transfers per person-year alive in the control arm will be between 1.06 and 2.12. Based on prior research; we estimate the absolute reduction in hospital transfer rates in the intervention vs. control NHs will range from .200 to .275 points, representing approximately a 16% relative reduction.

| Initial Hospital Transfer Rates/Year | Effect Size | | | |
|--------------------------------------|-------------|-------|------|-------|
| | 0.20 | 0.225 | 0.25 | 0.275 |
| 1.06 | 81 | 63 | 50 | 41 |
| 1.51 | 165 | 129 | 103 | 84 |
| 2.12 | 351 | 275 | 220 | 180 |

Computations for sample size estimates were performed using the approach for the comparison of incidence rates discussed in Chapter 5 of Donner & Klar and in Hayes & Bennett (1999). The sample size computation is based on a simplifying assumption of a Poisson distribution for the numbers of hospital transfers, and it assumes equal number of facilities in each arm. To achieve power of at least 90% in testing for

a .25 point absolute reduction in the observed average hospital transfer rate of 1.51, we will require 103 facilities per study arm. This represents approximately a 16% relative reduction in the hospital transfer rate.

Although our sample size calculations indicate that we require 103 NHs/arm, to accommodate the anticipated 10% non-participation rate among NHs randomized to the intervention arm, we will recruit an additional 16 facilities in the intervention arm for a total of 119 intervention NHs. Moreover, because there is an available total pool of 360 eligible facilities in our partner health systems, we will choose to assign the remaining 241 facilities to the control arm (approximate 2:1 control:intervention match) since there is no additional cost to do so. While more control facilities only marginally increases power it allows for a more precise estimate of the outcome of interest in the control group.

Data for 2012-13 from our partners reveal that there are, on average, 42 people meeting advanced dementia and/or CHF/COPD target criteria per facility. Thus, we estimate that there will be approximately 4,326 target patients in the 103 control NHs in (103*42=4,326) required by our aforementioned power calculation. In the actual assigned facilities, we estimate there will be 4998 patients meeting these criteria in 119 intervention NHs and 10,122 patients in the 241 control NHs.

9.2.2. Treatment Assignment Procedures: Please refer to *section 4* for a detailed description of the treatment assignment procedures.

9.2.3. Blinding: Our partner health care systems will know which facilities are designated intervention facilities, but will not be aware of those in the control group. Only Brown University statistician and data management staff will know the identity of the control facilities. They will present aggregated post-random assignment comparisons of intervention and control facilities' baseline characteristics, but these preliminary analyses will be not generated at the individual facility level. As [name] will be leading intervention training, he will be aware of the identity of the intervention NHs but will not be involved in data analyses activities. Drs. [name] and [name] will be blinded to the identity of both the control and intervention facilities. Facility assignment will be unblinded to the DSMB members at their request.

9.3. Interim Analyses and Stopping Rules

We are not including stopping rules in the PROVEN trial protocol for several related reasons. First, it is our contention that this is a minimal risk study for which serious negative reactions will be extremely rare (*see Section 7.1*). Second, a stopping rule would not be very feasible. The implementation period is only 24 months in each facility and the outcome observation period is 12 months for each target patient followed during that 24-month period. Final hospital transfer data may not be available for up to six months after the admission. Thus, differences in hospital transfer rates between the two study arms will not be known until the end of the 24-month study facility intervention period.

9.4. Outcomes

9.4.1. Primary outcome: The primary trial outcome is the hospital transfer rate (number of hospital transfers/person-day alive based on Medicare claims data), which include admissions, emergency department visits, and observation stays) over a 12-month follow-up period among Medicare fee-for-service among long-stay residents with advanced dementia or advanced CHF/COPD over 12 months (Aim 2).

9.4.2. Secondary outcomes: Secondary outcomes include: i. hospital transfer rates in the sub-groups examined in Aims 3 (short-stay patients with advanced dementia or advanced CHF/COPD) and Aim 4 (short-and long stay patients who do NOT have advanced dementia or CHF/COPD), and ii. The following outcomes for target sub-groups defined in Aims 2, 3, and 4: advance directives, burdensome treatments (e.g., tube-feeding), receipt of hospice services, and Medicare ACP billing codes.

All outcomes in the long-stay patient populations are calculated over a 12-month follow-up period. For short-stay patients, advance directive completion rates will be calculated over the admission period, and hospital transfer rates, use of burdensome treatments, and hospice enrollment will be examined within 100-days after the NH admission date.

9.5. Data Analyses

Aim 1: To implement all aspects of a pragmatic cluster RCT: Assessment of Aim 1 will largely be experiential and based on meeting planned recruitment milestones. We will assess the implementation of the ACP Video Program by examining data from the new Video Status Report

User Defined Assessment record created in the EMR that documents the videos offered. Descriptive statistics will be generated describing the proportion of the general NH population and targeted sub-populations exposed to the video, which videos they saw, who saw them (patient and/or family members), who showed the videos (nurse, physician, social worker), and the timing of exposure (i.e., relative to admission, discharge care planning meetings).

Aim 2 To evaluate the effectiveness of the ACP intervention among long-stay NH residents with advanced comorbid conditions: The sample includes long-stay residents with advanced dementia and advanced CHF/COPD. The primary trial outcome is the hospital transfer rate (number transfers/person-days alive based on Medicare claims data), which include admissions, emergency department visits, and observation stays) over a 12-month follow-up period among Medicare fee-for-service) in this cohort. Secondary outcomes include: advance directives (DNR, DNH, DNI, no tube-feeding), burdensome treatments (new feeding tube insertion, intubation, parenteral therapy, ICU care), hospice admission, and Medicare ACP billing codes. All outcomes will be 12-month incidence measures starting from the date residents are first identified as meeting the criteria for definitions of having advanced dementia or CHF/COPD during the 24-month intervention period. While we do not anticipate the ACP intervention to affect mortality,³¹ our analyses will account for censoring during the 12-month observation period. We will formally test for a mortality differential between intervention and controls arms using a logistic regression random effects model, where clustering is performed by facility.

Using current MDS data from CMS, we observe that the distribution of the primary outcome, hospital transfers, is over-dispersed with many of the patients having no hospital transfer over the 12-month follow up period. In addition, we also observed that hospital transfer rates vary across facilities, even after adjusting for underlying patient risk. To account for these phenomena, we will utilize a zero-inflated Poisson distribution with facility random effects to test and estimate the effects of the ACP intervention. Zero-inflated Poisson models have been used in other public health settings.^{128, 129} Formally, let Y_{ij} be the number of hospital transfers for person i in facility j , N_{ij} is the number of person days alive for person i in facility j , and T_j is a treatment indicator that is equal to one if facility j is in the intervention group. Then where β_1 is the conditional increase in the log hospital transfer rate in facilities that receive treatment vs. those that do not, and α_1 is the conditional log odds ratio for being hospitalized vs. never being hospitalized in the intervention vs. the control arm. When both α_1 and β_1 are smaller than 0, the ACP video is effective in reducing the proportion of patients hospitalized and the number of times hospitalized. Using this model we will estimate the marginal average hospital transfer rate in each arm and calculate the difference between the two arms. We will use a two sided test to examine if the marginal average difference is significantly different than zero, and we will calculate the corresponding interval estimate. As a secondary analysis, we will use the likelihood ratio test to compare the null hypothesis, $H_0 : \alpha_1 = \beta_1 = 0$, to the alternative hypothesis $H_1 : \alpha_1 \neq 0$ or $\beta_1 \neq 0$.¹³⁰ Confidence intervals for α_1 and β_1 can be obtained by inverting the likelihood ratio test.¹³² This analysis will enable us to provide additional details as to whether the effectiveness of the intervention is to reduce the likelihood of one hospital transfer or the number of hospital transfers if transferred at least once.

The secondary outcomes are binary. Commonly used methods applied to the analysis of clustered RCT with binary outcomes are GEE and multilevel models.¹³¹ The former method provides a population “average” effect, while the latter results in a conditional cluster effect. For continuous Gaussian data, interpretation of the treatment coefficient

$$\begin{aligned}
 p(Y_{ij} = 0) &= \phi_{ij} + (1 - \phi_{ij}) \exp^{-\theta_{ij}} \\
 P(Y_{ij} = y) &= (1 - \phi_{ij}) \frac{\exp^{-\theta_{ij}} \theta_{ij}^y}{y!} \quad y = 1, 2, \dots \\
 \text{logit}(\phi_{ij}) &= \alpha_0 + \alpha_1 T_j + u_j \quad u_j \sim N(0, \sigma_u^2) \\
 \text{log}(\theta_{ij}) &= \beta_0 + \beta_1 T_j + \log(N_{ij}) + v_j \quad v_j \sim N(0, \sigma_v^2)
 \end{aligned}$$

is the same in conditional and marginal models; however, with binary data, the treatment coefficient from a marginal model is smaller than that from a conditional model and has a different interpretation.¹³² For binary outcomes, Bellamy et al¹³³ have shown that with few clusters GEE results were more likely to reject the null hypothesis, while conditional models resulted in more conservative estimates. Austin concluded that the power of GEE and multilevel models are very similar for studies, like ours, that include more than 30 clusters (facilities) with either variable or equal cluster size.¹³⁴ To estimate the effect of ACP on secondary outcomes we will use random effects logistic model. Formally, let S_{ij} one of the secondary outcomes for person i in facility j , and T_j is a treatment indicator that is equal to one if facility j is in the treated arm.

$$\begin{aligned}
 S_{ij} &\sim \text{Ber}(p_{ij}) \\
 \text{logit}(p_{ij}) &= \gamma_0 + \gamma_1 T_j + \zeta_j \\
 \zeta_j &\sim N(0, \sigma_\zeta^2)
 \end{aligned}$$

where γ_1 is the conditional log odds ratio for observing the secondary outcome in the treatment arm vs. the control arm. When γ_1 is smaller than 0, ACP is effective. As for the primary outcome we will use the likelihood ratio test the null hypothesis $H_0 : \gamma_1 = 0$, and by inverting this test we will obtain the corresponding confidence interval.

Aim 3. To evaluate the effectiveness of the ACP intervention among new admissions to post-acute care with the advanced comorbid conditions: Newly admitted NH patients to post-acute care with advanced dementia or advanced CHF/COPD disease will accrue throughout the 24-month intervention. Measured outcomes for this group will include: advance directives to withhold specific treatments (DNH, DNR, DNI, no tube-feeding) at any time during their post-acute care admission, hospital transfers, and hospice enrollment within 100 days following NH admission. Preliminary data found that 100-day hospital transfer rates among post-acute patients with advanced dementia and/or CHF/COPD was 37%, and that nearly 50% of advanced dementia and 30% of advanced CHF/COPD patients died within 6 months of NH admission. In light of the high mortality rate, we will adopt the hospital transfers per person-day alive approach described for Aim 2 to evaluate the effectiveness of the intervention.

Aim 4. To evaluate the effects of the ACP intervention among long-stay and new admissions to post-acute care WITHOUT advanced dementia or COPD/CHF: The intervention is being implemented facility-wide, thus all long-stay residents and post-acute care admissions will be exposed to it. Aim 4 tests the impact of the intervention on NH patients WITHOUT

$$p(Y_{ij} | X_{ij}) = \begin{cases} \pi_{ij} + (1 - \pi_{ij}) \exp(-\mu_{ij}) & Y_{ij} = 0 \\ (1 - \pi_{ij}) \frac{\exp(-\mu_{ij}) \mu_{ij}^{Y_{ij}}}{Y_{ij}} & Y_{ij} \geq 0 \end{cases}$$

advanced dementia or advanced CHF/COPD. Outcomes include: advance directives during their NH stay, the number of hospital transfers over 12-months for long-stay or over 100 days for short-stay; and hospice admission over 12 months for long-stay or over 100 days for short-stay. As hospital transfers and hospice enrollment among post-acute care patients are likely to occur after NH discharge, these outcomes can only be assessed among the fee-for-service Medicare beneficiaries using Medicare claims. The outcome, Y_{ij} , is a total count of hospital transfers. Many relatively healthy patients will have $Y_{ij}=0$ while others' hospital use depends on the number of days that they are alive. We will use a zero-inflated Poisson model^{135, 136} of the following form shown in the equation, where $\text{logit}(\pi_{ij}) = X_i\beta + \eta T_i + \delta_{ij}$, X_i are the covariates, η is the treatment effect, and $\varepsilon_{ij} \sim N(0, \sigma_\pi)$ is a random between facility effect. When η is larger than 0 and λ is smaller than 0, ACP video is effective. The same analytic approach described for Aim 2 will be used to evaluate the effectiveness of the intervention.

Sub-Group Analyses of Racial and Ethnic Group Differences in Intervention Effects: It is well-recognized that African-American NH patients with advanced illness are more likely than white patients to have outcomes reflecting more aggressive care, including higher hospitalization rates and lower advance directive documentation rates, even after controlling for patient and facility factors. Nonetheless, there is no evidence suggesting that African American patients respond differently to our ACP intervention than white residents. In fact, the videos have been specifically designed to be appropriate to viewers from all backgrounds

Based on existing data, we anticipate only 11% of the patients included in our analyses will be African-American, and even lower proportions will be of other non-white racial and ethnic groups. Thus, there will not be sufficient power to detect small differences in outcomes among non-white groups. Consequently, these sub-group analyses are necessarily exploratory. Nonetheless, we will conduct sub-group analyses for Aim #2 separately among African-American residents and other racial/ethnic groups (e.g., Hispanic) if numbers allow. Additionally, we will examine differences in video viewing rates among racial and ethnic groups.

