H3c: A higher proportion of post-acute care in the intervention (vs. control) NHs will be enrolled in hospice.

Aim 4: To evaluate the effects of the ACP intervention by comparing outcomes (advance directive orders, hospital transfers, hospice use, and Medicare ACP billing codes) in the intervention vs. control NHs among long-stay residents and newly admitted post-acute care patients who do NOT have designated advanced illness (i.e., dementia, CHF, or COPD).

H4a: A higher proportion of NH patients without advanced dementia, COPD, or CHF in the intervention (vs. control) NHs will acquire advance directives to withhold specific treatments.

H4b: Hospital transfers will be lower among NH patients without advanced dementia, COPD, or CHF in the intervention (vs. control) arms.

H4c: A higher proportion of NH patients without advanced dementia, COPD, or CHF in the intervention (vs. control) NHs will be enrolled in hospice.

Exploratory Aim: Among decedents, to compare the proportion of patients in the intervention and control facilities who had any of the following interventions in the last month of life: hospital transfer or other burdensome interventions (feeding tube insertion, parenteral therapy, intubation, ICU care). Separate analyses will be done among decedents from the short and long-stay cohorts with advanced dementia, CHF or COPD, as well as those without advanced disease.

Cohort and outcomes specifications:

A. Hospital transfer outcome

1. For all analyses involving this outcome, including the primary trial outcome, the main analyses will be restricted to Medicare Fee-for-Service patients because ascertainment of hospital transfers is most accurate from Medicare Claims data. Exploratory analyses will also be done on all patients, not just FFS, using the MDS as well as Medicare claims as the data sources.
2. For the primary outcome and all relevant secondary outcomes, ‘hospitalizations’ was modified to ‘hospital transfers’ based on Medicare claims data, which include admissions, emergency department visits, and observation stays. This change was made so as to capture the main “decision” to send a patient from the nursing home to the hospital.

B. Advance directive outcome

1. For all aims, advance directives analyses will be limited to Genesis facilities in which >75% of patients have any advance directive because the remaining Genesis and Pruitt facilities do not have reliable sources for these data.

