2. The proportion of residents in a facility whose last observed advance directive status during their observation period was DNR, DNH, DNI or feeding restrictions
 - i. The proportion of short-stay residents in a facility whose last observed advance directive status during their 100-day observation period was DNR, DNH, DNI or feeding restrictions
 - ii. The proportion of long-stay target residents in a facility whose last observed advance directive status during their 12-month observation period was DNR, DNH, DNI or feeding restrictions
 - iii. The proportion of long-stay non-target residents in a facility whose last observed advance directive status during their 12-month observation period was DNR, DNH, DNI or feeding restrictions
3. Among participants who are full code when they become part of the study (on admission to a NH), the average time to switching from full code to DNR, DNH, DNI or feeding restrictions during a 12-month observation period.

C. Burdensome interventions

1. For Aim 2.3, burdensome interventions will include: new feeding tube insertions (i.e., did not have a feeding tube at start of observation period), parenteral therapy (for hydration or medication delivery), intubation, or ICU care). The outcome will be analyzed as the proportion of long-stay target cohort residents that had any burdensome intervention during the 12-month observation period.

D. Hospice:

1. In the long-stay target cohort, the proportion of residents with any Medicare hospice claim in the 12-month observation period.
2. In the non-target long-stay cohort, the proportion of residents with any Medicare hospice claim in the 12-month observation period.
3. In the short-stay cohort without advanced comorbid conditions, the proportion of residents with any Medicare hospice claim in the 100-day observation period.
4. In the short-stay cohort with advanced comorbid conditions, the proportion of residents with any Medicare hospice claim in the 100-day observation period. For both long-stay and short-stay cohorts, residents on hospice at the start of the observation period will be excluded.

E. Medicare Advance Care Planning Billing

1. In long-stay target cohort, the proportion of residents with any Medicare ACP billing code in the 12-month observation period.
2. In non-target long-stay cohort, the proportion of residents with any Medicare ACP billing code in the 12-month observation period.

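### The advance directive outcome follows conflicting rules within each cohort, and orders that predate the videos are counted without any term for them in the model

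*Combined protocol and SAP*

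**What the plan says.** **Long-stay target cohort.** Section 9.5 (Aim 2) lists advance directives among the secondary outcomes and then states: "All outcomes will be 12-month incidence measures starting from the date residents are first identified as meeting the criteria". Section 1, item B.2, defines the outcome differently: "The proportion of residents in a facility whose last observed advance directive status during their observation period was DNR, DNH, DNI or feeding restrictions". Item B.2.ii applies this to "long-stay target residents in a facility whose last observed advance directive status during their 12-month observation period".

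**Short-stay patients.** Item B.2.i counts "short-stay residents in a facility whose last observed advance directive status during their 100-day observation period" was one of the listed orders. Section 9.4.2 says "For short-stay patients, advance directive completion rates will be calculated over the admission period", and keeps 100 days for the other short-stay outcomes. Section 9.5 (Aim 3) counts orders "at any time during their post-acute care admission".

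**Hypotheses.** H4a expects that more patients "will acquire advance directives to withhold specific treatments". H2a and H3a speak of having orders, not of acquiring them.

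**Orders present at entry.** B.2 has no rule for them. In the same list, the hospice outcome leaves out residents already on hospice, and the feeding-tube component counts new tubes only. Item B.3 is a separate measure: time to switching among residents who were full code on admission. The random-effects logistic model in Section 9.5 has only a treatment indicator and a facility effect. Section 9.1 allows adjustment for small imbalances where required, without naming directive status.

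**The concern.** Two rules stand for one outcome in each cohort, and they classify some residents differently. With no stated priority, the analyst must choose, possibly after seeing data.

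The second issue is what the last-status and any-time rules count. An order written before anyone could have been offered a video says nothing about the intervention. Counted as a success in both arms, it can shrink the absolute difference, pull the odds ratio towards 1, and bring in differences between facilities that predate the trial. A covariate for the earlier order would absorb much of that variation, but the plan does not provide one.

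**Working it through.** The plan gives no baseline rate, effect size or power for this outcome, so there is no figure to reproduce.

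**Step 1. Score the same histories under each rule.**

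| History | Incidence (9.5, long-stay target) | Last status (Section 1, both cohorts) | Any time (9.5, short-stay) |
|---|---|---|---|
| Order before entry, kept | not a case | success | success |
| No order at entry, gained and kept | case | success | success |
| No order at entry, gained then reversed | case | not a success | success |
| Order at entry, then reversed | not a case | not a success | success |

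In the long-stay target cohort, the incidence and last-status rules disagree on the first and third rows. In the short-stay cohort, last status and any time disagree on the third and fourth rows, and the windows differ as well (100 days or the admission). Both of these rules count the first row.

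**Step 2. Size of the dilution.** Let p0 be the proportion with the order before exposure, equal in both arms, and let ic and it be the control and intervention risks of a new order among the rest. If earlier orders are kept equally in both arms, they cancel in the difference:

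last-status risk difference = (1 − p0) × (it − ic).

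The values of p0 in the first five rows are the background figures in Section 2.2, which are not from the trial cohort. The new-order risks of 10% and 15% are assumed (difference 5.0 points, odds ratio 1.59). The odds ratios below also assume that all earlier orders are kept.

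| Order and population | p0 | Factor 1 − p0 | Last-status difference (points) | Last-status odds ratio |
|---|---|---|---|---|
| DNH, post-acute | 2% | 0.98 | 4.90 | 1.50 |
| DNH, nursing home | 4% | 0.96 | 4.80 | 1.43 |
| No tube-feeding, nursing home | 11% | 0.89 | 4.45 | 1.30 |
| DNR, post-acute | 32% | 0.68 | 3.40 | 1.15 |
| DNR, nursing home | 52% | 0.48 | 2.40 | 1.10 |
| If the facility filter in B.1 refers to orders to withhold | 75% | 0.25 | 1.25 | 1.08 |

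For DNR at 52%: control 0.52 + 0.48 × 0.10 = 0.568; intervention 0.52 + 0.48 × 0.15 = 0.592; difference 0.024. The last row is a bound: B.1 keeps facilities where more than 75% have any directive, and it is unclear whether a recorded full code counts.

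**Step 3. Precision, for DNR at 52%.** Assume a two-sided 5% level and borrow the 90% power stated for the primary outcome, with independent residents and no design effect. Detecting 10% against 15% needs 918 per arm without an order, that is 918 / 0.48, about 1,913 residents of either status. Unadjusted last status needs 8,886 per arm, a ratio of 4.65. The ratio runs from 7.4 (5% against 10%) to 2.6 (20% against 30%).

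**Step 4. When the shrinkage fails to appear.** Keep p0 = 52% and new-order risks of 10% and 15%.
- Retention of earlier orders 95% in control and 100% in intervention: 0.52 × 0.95 + 0.048 = 0.542 against 0.52 + 0.072 = 0.592, a difference of 5.0 points.
- Earlier video exposure raises the share with an order at target-cohort entry from 52% to 57%: 0.568 against 0.57 + 0.43 × 0.15 = 0.6345, a difference of 6.65 points.

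**The case against.** The best defence is that B.2 is a deliberate, cohort-by-cohort specification and can be read as governing, with the sentence in Section 9.5 as loose summary wording. H2a and H3a fit that reading. The short-stay mismatch may also be small in practice: directives come from the facility record only (Table 2), and short-stay means under 90 days. A 100-day window and the admission then largely coincide apart from readmissions, and last status differs from any time only when an order is reversed. B.3 already analyses residents without an order on admission.

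Much of this stands. A reader might infer that three rules collide in a single cohort. They do not: there is one conflict in the long-stay target cohort and another among short-stay patients. A reader might also infer that videos can only create orders, so that last status must understate the effect. The documents do not support that. Videos are offered again every six months and at changes in status (Section 5.2), and the goals-of-care video presents intensive care as one option (Section 5.1). Orders may therefore be kept or reversed because of them, and last status captures this.

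What does not stand is that the plan already settles the matter. No section gives B.2 priority. B.3 is a time-to-switch measure and omits a resident who enters with DNR and later gains DNH. If B.2 is read as a composite, that resident is a success from the start. Adjustment where required, without naming directive status, does not commit anyone to the relevant covariate.

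**Conclusion.** The contradictions are in the current text and need no assumed figure. This is a secondary-outcome problem that should be corrected; the primary outcome is unaffected.

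The dilution is conditional. It rests on earlier orders being equally common and equally retained in the two arms. On the background figures the factor is about 0.48 for DNR in nursing home patients, 0.68 for DNR in post-acute care, 0.89 for no tube-feeding and 0.96 for DNH. The loss matters mainly for DNR or a composite containing it. Prevalence in the trial cohort is not given, so the actual size is unknown.

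It is tempting to conclude that the main analysis should count first new orders from target-cohort entry. The plan's own design argues against that. Long-stay residents can convert to the target cohort during implementation (Section 4.2), after an offer at admission (Section 5.2). An order they already hold on conversion may be an effect of the intervention. Excluding it would condition on a post-randomisation event, and a window that opens at conversion would score it as a non-event.

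**What to change.** 1. Name one governing definition and window per cohort, and use it in Sections 1, 9.4.2 and 9.5. The simplest choice is last observed status, separately for DNR, DNH, DNI and no tube-feeding. Exempt advance directives from the incidence sentence in Section 9.5, and choose one short-stay window.
2. Add to the logistic model a term for whether the same order was present before exposure. Take it at nursing home admission, or at one common calendar date before the first training wave if that is later. Define it identically in both arms: control facilities have no start date, and intervention facilities began in four waves. Do not use status at target-cohort entry.
3. As a supporting analysis, report new orders among residents without that order at the pre-exposure date. Count any order gained from that date, so that orders obtained before conversion are not missed.

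The term gives an odds ratio between residents of like prior status and removes variation that predates the trial. It does not enlarge the risk difference over all residents; the difference among those without an order comes from item 3.

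The cost is mainly SAP wording and one derived variable. B.3 already presupposes code status on admission, but dated status by order type needs to be confirmed in the records of the facilities kept under B.1. Residents with no recorded pre-exposure status need a missing category, and the supporting analysis uses fewer residents.
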